#### **9. ADVERSE EVENTS**

The Investigator is responsible for detection and documentation of events meeting the criteria and definition of an AE/SAE as provided in this protocol. At each safety evaluation during the study, the Investigator or designee will collect information on unusual manifestations or AEs and SAEs and will record them on the AE page of the eCRF. Their nature, severity, duration, treatment, and relationship with the IMPs as assessed by the Investigator will be recorded. The Investigator will also indicate whether study treatment was discontinued and how the event evolved.

## 9.1. Definitions and assessment criteria

### 9.1.1. Adverse event

An AE is any untoward medical occurrence in a patient or clinical trial patient administered a medicinal product and which does not necessarily have a causal relationship with this treatment.

Thus, any new sign, symptom or disease, or any clinically significant worsening of an existing sign, symptom or disease compared to the condition at the first visit (including disease treated), should be considered as an AE. Lack of efficacy is not considered as an AE.

In particular:

- Any new sign or symptom reported by the subject that appears after accidental or intentional overdose or misuse should be reported as an AE.
- Whenever possible, a diagnosis should be reported on the AE form, instead of signs, symptoms or abnormal laboratory values.
- Pregnancy is not to be considered as an AE; however, it must be monitored as described in [Section 9.5](#).
- Each new episode of a chronic disease (e.g., hay fever, allergy, etc.) from the screening visit should be reported as a new AE.

AEs are illnesses, signs or symptoms (including abnormal laboratory findings) occurring or worsening in the course of the study. AEs can be serious or non-serious. They may or may not lead to the withdrawal of the patient from the study.

### 9.1.2. Serious adverse event

A SAE is defined as any untoward medical occurrence that at any dose:

- Results in death;
- Is life threatening (i.e., puts the patient at immediate risk of death);
- Requires inpatient hospitalisation or prolongation of existing hospitalisation;
- Results in persistent or significant disability/incapacity;
- Is a congenital anomaly/birth defect, or
- Is otherwise medically significant: Important medical events that may not immediately be life threatening or result in death or hospitalisation, but that jeopardize the patient or require intervention to prevent one of the outcomes listed in the definitions above shall also be considered as serious.

All AEs that do not correspond to the definition of SAE are considered as non-serious.

### 9.1.3. Unexpected or expected adverse events

An unexpected AE is an event whose nature or severity is not consistent with information on the condition under study and/or not consistent with the applicable product information, i.e. the Investigator Brochure.

All AEs that are suspected to be related to the IMP(s) and that are both unexpected and serious are considered to be Suspected Unexpected Serious Adverse Reactions (SUSARs).

### 9.1.4. Severity of adverse events

AEs will be graded by the Investigator or designee according to NCI-CTCAE, version 5.0.

If a particular AE's severity is not specifically graded by this guidance document, the Investigator is to revert to the general definitions of grades 1 to 5 and to use his or her best medical judgment:

- **Grade 1 (mild):** Causing no limitation of usual activities, the patient may experience slight discomfort.
- **Grade 2 (moderate):** Causing some limitation of usual activities, the patient may experience annoying discomfort.
- **Grade 3 (severe):** Causing inability to carry out usual activities, the patient may experience intolerable discomfort or pain.
- **Grade 4:** Life-threatening
- **Grade 5:** fatal

### 9.1.5. Relatedness to IMPs

The Investigator or designee will determine the relationship between the AE and the IMPs according to the following criteria:

#### Reasonable causal relationship:

A clinical event, including laboratory test abnormality,

- Where time relationship to drug administration is at least reasonable, and
- Where other causes (e.g. underlying disease) may not by themselves explain the event, and/or
- Where a clinically reasonable response occurs on withdrawal (dechallenge).

#### No reasonable causal relationship:

A clinical event, including laboratory test abnormality,

- Where time sequence to drug administration is not reasonable, or
- Where other causes (e.g. underlying disease) can by themselves provide plausible explanations.

### 9.1.6. Adverse events of special interest

AESIs are

1. for Debio 1143:
  - a. AST or ALT increases >3 ULN associated with total bilirubin >2 ULN and ALP <2 ULN
  - b. Lipase or amylase increases >5 ULN
  - c. Any QTcF prolongation above 30 ms compared to baseline on at least two consecutive readings or other ECG abnormalities such as Torsade de Pointe, ventricular tachycardia, ventricular fibrillation, flutter or any other new cardiac abnormality at the ECG or during the physical examination considered as clinically significant.
2. for nivolumab:
  - a. Any AEs that are suspected to be immune-related or infusion-related including drug hypersensitivity, immune-related pneumonitis, immune-related colitis, immune-related hepatitis, immune-related endocrinopathies such as: thyroid disorders, adrenal insufficiency, new onset type I diabetes mellitus, pituitary disorders; or immune-related

nephritis and renal dysfunction and other immune-related AEs such as: myositis, myocarditis, Guillain-Barré syndrome or uveitis of any grade

All AESIs, occurring after treatment start on C1D1 must be reported to the sponsor in the appropriate eCRF pages. When reporting these cases, it has to be specified in the eCRF whether the case is serious or non-serious. If the AESI(s) is/are serious or considered to be a DLT, then it has to be properly reported within 24 hours of acknowledgement and all applicable SAEs reporting guidelines should be followed (as described in [section 9.2](#)) including the reason why it is considered serious.

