**Table 5-3 Re-treatment criteria**

Assessment	Debio 1143		Nivolumab
	Days 1 and 15	Days 2-10 or 16-24	Days 1 & 15
ECOG-PS	≤1	≤2	≤1
ANC	≥ 1.5 x10  /L	≥ 1.0 x10  /L	-
Platelets	≥ 100 x10  /L	≥ 75 x10  /L	-
Hemoglobin	≥ 9.0 g/dL	≥ 9.0 g/dL	≥ 9.0 g/dL
Total bilirubin	grade 1	grade 2 a	grade 1
AST/ALT	grade 1	grade 2 a	grade 1
Amylase or lipase increases	≤ Grade 3 b		-
Serum creatinine	≤ 2.0 x ULN	-	≤ 2.0 x ULN
Non-optimally treated, symptomatic immune-related AEs	-		≤ Grade 1 c
Any Debio 1143 drug-related AEs	≤ Grade 1 c	≤ Grade 2	-
Cardiac safety/ ECG	Baseline status		
βHCG urine pregnancy test (for women of childbearing age) d	Negative	-	Negative

ANC: absolute neutrophil count; AST/ALT: aspartate aminotransferase/alanine aminotransferase; AEs: adverse event(s); ECG: electrocardiogram; ECOG-PS: Eastern Cooperative Oncology Group performance status

- Provided that total bilirubin and/or ALT/AST levels were Grade 1 as per NCI-CTCAE v5.0 at the start of the corresponding cycle.
- As per NCI-CTCAE v5.0, Grade 3 is defined as amylase or lipase increases up to 5x ULN symptomatic or not; or above 5x ULN but asymptomatic
- Up to Grade 2 for alopecia, stable sensory neuropathy, fatigue/asthenia, skin toxicity or non-optimally treated nausea, vomiting or diarrhea or any grade endocrinopathy optimally treated by replacement therapy
- On every Day 1 for both Debio 1143 and nivolumab

From Cycle 2, if a patient does not meet the requirements for treatment continuation on Day 1 of any cycle, both study drugs will be withheld until recovery or for a maximum of 4 and 8 weeks (+1 week tolerance window) for Debio 1143 and nivolumab, respectively. After this delay-period, treatment should be withdrawn. If a delay occurs in initiating Cycle 2 and is due to any toxicity related to study drug, it will be considered as a DLT.

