#### 8.2.2.4. 12-lead ECG

High-quality, digital triplicate 12-lead ECGs will be recorded after 10 minutes of supine rest at screening. High-quality, digital triplicate 12-lead ECGs will be recorded after 10 minutes of supine rest on Day 1 of Cycle 1 and Cycle 3 and on Days 8, 15 and 22 of Cycle 1 at the following 3 time points: pre-, 0.5-2h Debio 1143 post-dose (before starting the nivolumab infusion or after nivolumab perfusion was removed) and 4-6 h post-dose. ECG readings must be performed prior to PK/PDy sampling. There should be at least 1 minute between each ECG and all 3 ECGs should be completed within 10 minutes. Reading will be done centrally by a dedicated team. For eligibility purposes, the screening reading will be done also locally by the investigator or a cardiologist will be consulted if clinically indicated.

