18.1.16. ADVERSE EVENTS OF SPECIAL INTEREST (AESIs)

AESIs (as described in protocol section 9.1.6) are AEs recorded on the eCRF where “Is this an adverse event of special interest” is answered as “yes”.

Treatment-emergent AESIs will be presented by the following:

- SOC/PT & by cycle
- SOC/PT & worst grade

A vertical bar plot will be produced showing the number of patients experiencing an AESI presented by worst grade and by cycle.

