18.3.1. LABORATORY SPECIFIC DERIVATIONS

No specific laboratory derivation will be performed.

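### The Debio 1143 AESIs are largely numeric, but the SAP counts only those ticked on the eCRF and plans no derivation from laboratory or central ECG data; the liver pattern has no other output that would show it

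*Protocol*

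**What the plan says.** Protocol 9.1.6 lists three AESIs for Debio 1143:

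- **1a, liver:** "AST or ALT increases >3 ULN associated with total bilirubin >2 ULN and ALP <2 ULN".
- **1b, pancreas:** "Lipase or amylase increases >5 ULN".
- **1c, cardiac:** "Any QTcF prolongation above 30 ms compared to baseline on at least two consecutive readings or other ECG abnormalities". Named arrhythmias and any other new cardiac finding judged clinically significant follow.

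So 1a and 1b are wholly numeric, and 1c has one numeric limb (QTcF) and one that needs judgement. The same section obliges sites to enter every AESI arising after C1D1 in the eCRF.

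SAP 18.1.16 sets the counting rule: "AESIs (as described in protocol section 9.1.6) are AEs recorded on the eCRF where" the AESI question is answered yes. The two AESI tables (SOC/PT by cycle, SOC/PT by worst grade) and the bar plot all use that flagged set. On laboratory data, SAP 18.3.1 states: "No specific laboratory derivation will be performed". SAP 18.3 summarises each analyte separately. SAP 18.4.1 classifies QTcF increases above 30 and above 60 msec, using each replicate of the triplicate.

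**The concern.** A numeric definition can be evaluated for every patient from the database. The SAP instead makes the count depend on a site recognising the pattern, entering it as an AE and ticking a box. There are plausible ways to miss that step. Protocol 9.1.1 asks that, where possible, "a diagnosis should be reported on the AE form, instead of signs, symptoms or abnormal laboratory values", so a bare laboratory pattern may not be entered as an AE in its own right. For on-treatment ECGs, Protocol 8.2.2.4 says "Reading will be done centrally by a dedicated team"; it adds a local reading only for screening eligibility, and it does not describe how central results return to the site.

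Safety and tolerability at the RP2D are a Part B secondary objective, and these are the events the sponsor singled out for Debio 1143. In Part A, a closely similar liver pattern is also a DLT criterion (Protocol 5.2), which gives a second route to notice it. Part B has no DLT analysis, so the AESI tables carry more of the weight there.

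**Working it through.** The plan gives no figure to reproduce. The check is to trace each numeric criterion from its definition to the output that would show a case the site did not tick.

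**Are the data collected?** Yes. Total bilirubin, ALP, AST, ALT, amylase and lipase are in the chemistry panel (Protocol 8.2.2.5). Triplicate ECGs are scheduled at three time points on C1D1, C1D8, C1D15, C1D22 and C3D1 (Protocol 8.2.2.4): 5 × 3 × 3 = 45 tracings per patient. Removing the 3 pre-dose tracings on C1D1 leaves 42 after the first dose.

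**What does the flagged count measure?** Reported AESI patients = (qualifying and ticked) + (ticked but not qualifying). The documents give no value for the proportion of qualifying patients who are ticked, nor for false ticks, so the net error cannot be calculated.

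**1a, liver.** Table 7-2 of the protocol, under its NCI-CTCAE v5.0 heading, gives grade 2 as AST or ALT >3 to 5×ULN and total bilirubin >1.5 to 3×ULN when baseline is normal. Setting these against the AESI limits:

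- AST/ALT: values >3×ULN that are also grade 2 are >3 to 5×ULN, which is the whole grade 2 range.
- Bilirubin: values >2×ULN that are also grade 2 are >2 to 3×ULN.

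A patient in both ranges with ALP <2×ULN meets 1a while being only grade 2 on each analyte. The SAP 18.3 listing of notable abnormalities takes newly occurring grade 3 or 4 values only, so this patient is not in it. The single-analyte shift tables show a grade 2 AST/ALT and a grade 2 bilirubin, but not that they belong to the same patient at the same time. No output combines AST/ALT, bilirubin and ALP. Only cross-reading the full laboratory listing would find the case.

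Grade and ULN multiple can also diverge. Table 7-2 grades by multiples of baseline when baseline is abnormal, and inclusion criterion 9 admits AST/ALT up to 5×ULN with liver metastases. For a baseline of 5×ULN, grade 1 extends to 3 × 5 = 15×ULN.

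**1b, lipase/amylase.** Footnote b of Table 5-3 says "Grade 3 is defined as amylase or lipase increases up to 5x ULN symptomatic or not; or above 5x ULN but asymptomatic". A value above 5×ULN is therefore grade 3 if asymptomatic and, by implication, higher if symptomatic. Unticked cases appear in the grade 3/4 outputs, but together with grade 3 values at or below 5×ULN. SAP 18.3.3 also has these two analytes reported by the investigator's grade, so the fallback is not independent of site judgement.

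**1c, QTcF limb.** Any patient above 30 ms on two consecutive readings has at least one replicate above 30 msec, so SAP 18.4.1 captures every such patient. It also captures patients with a single isolated replicate, because the consecutive-readings condition is not applied. The ECG shift table in SAP 18.4 covers absolute values only.

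| Criterion | In AESI incidence if unticked? | Where else it shows |
|---|---|---|
| 1a | No | Separate analyte tables and full listing; no combined output |
| 1b | No | Grade 3/4 outputs, mixed with values up to 5×ULN |
| 1c QTcF | No | >30 msec flags, mixed with single replicates |

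**The case against.** The strongest reply is that Protocol 9.1.6 makes AESIs a mandatory reporting item, so counting what was reported is consistent with the protocol. Behind it stands Protocol 11.2.1: automatic checks, queries, ongoing medical review of safety data, and reconciliation of external data against the eCRF. Central ECG data could well fall under that reconciliation. The liver pattern is hard for a site to overlook, since AST/ALT and bilirubin govern re-treatment and a closely similar pattern, when related to Debio 1143, triggers a dose reduction under Protocol 5.4. All of this stands, and it makes missed ticks less likely. None of it names the AESI criteria or changes the counting rule in SAP 18.1.16.

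Several stronger readings are tempting, and the documents do not support them:

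- **The SAP prohibits laboratory derivations.** SAP 18.3.1 says that no specific one is planned. CTCAE grades, shifts and recovery times are still derived, and the sentence does not concern ECG data.
- **Unticked cases vanish from the report.** They are missing from the AESI incidence. The 1b and 1c cases remain within broader outputs, and 1a remains in the listings.
- **The error can only be downward.** A site may also tick an event that falls short of the limit. Missed cases are the more natural worry, but the net direction is not established.
- **Sites never see on-treatment ECGs.** Table 5-3 makes baseline ECG status a re-treatment condition and Table 7-2 asks sites to act on an abnormal ECG, so some local knowledge is presupposed.
- **Sites are told not to report laboratory values.** The Protocol 9.1.1 instruction is qualified, and that section counts abnormal laboratory findings among AEs.

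**Conclusion.** The point holds as a gap in method. Three criteria fixed by number are counted only through an investigator flag, and no derivation or AESI-specific reconciliation is planned. It matters most for 1a, where an unticked case can be grade 2 on both analytes and appear in no combined or notable-abnormality output. For 1b and the QTcF limb of 1c the loss is one of precision: the cases can be seen but not isolated.

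The size of any undercount is unknown. A reader might want to attach a miss rate or work from 60 patients. The documents give no basis for a miss rate, and 60 is only the planned maximum of evaluable Part B patients, while SAP 4.3 already refers to the futility of the Part B cohorts. The conclusion rests on one modest assumption, that sites may sometimes fail to tick a qualifying event. The primary endpoints are not affected. This is an inexpensive improvement worth making.

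**What to change.** In SAP 18.1.16, 18.3.1 and 18.4.1:

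1. Derive 1a and 1b from the laboratory data, and the QTcF limb of 1c from the central ECG data, for every treated patient.
2. State the operating rules, agreed with the sponsor's medical team: what time link makes the liver values *associated*, how an abnormal baseline is handled, and whether consecutive *readings* means replicates or time points. The protocol leaves these open.
3. Report the number of patients meeting each criterion, by dose (Part A) and cohort (Part B), beside the investigator-flagged AESIs.
4. Query every mismatch, in either direction, before database freeze, within the data review already described in Protocol 11.2.1.
5. Leave the judgement-based parts of 1c to the investigator flag.

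The cost is SAP wording, a small amount of programming and some queries. No visits or samples are added and patient management does not change. AESI counts may come out slightly higher.

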## 9.2. Reporting of serious adverse events to the Sponsor

### 9.2.1. Reporting during the study

The Investigator must notify the Sponsor/Clinical Research Organization (CRO) of all SAEs within 24 hours of awareness by completing the AE form provided in the eCRF. Once the AE is selected as a Serious event and the form is saved in the eCRF an email notification will be sent automatically to the Sponsor's Pharmacovigilance department.

If for any reasons the eCRF is not available, as a back-up option the SAE can be declared by e-mail using the Debiopharm International (DPI) paper 'SAE Report form', or by telephone.

1. When reported by e-mail, the 'SAE Report form' will be sent to the following e-mail address: [REDACTED] ([REDACTED]) or CRO email address if applicable.
2. When reported by telephone, the DPI Pharmacovigilance Officer will be notified as specified in the site study file.

This should be followed by the completion of the AE form in the eCRF as soon as possible

The processes are fully described in separate guidelines and will be provided to investigators with the protocol.

Notification of SAEs does not depend on their relationship with the IMP(s). All SAEs regardless of their relationship with the study drugs and occurring until the last study visit will be reported as described above.

### 9.2.2. Reporting post-study

Any SAE occurring up to 5 months from the last nivolumab infusion date will be reported in the appropriate eCRF pages and within one day of SAE awareness as described in [section 9.2.1](#)

## 9.3. Follow-up of serious adverse events

All SAEs, regardless of severity, must be followed up:

- To resolution (the patient's health has returned to the baseline status or all variables have returned to normal), or
- Until stabilization of the event has occurred (the Investigator does not expect any further improvement or worsening of the event), or
- Until the event is otherwise explained regardless of whether the patient is still participating in the study.

Some events, such as metastases, are often ongoing; however, once these events have been determined by the principal Investigator to be stable or chronic, he/she may consider the event to be resolved or resolved with sequelae.

The Investigator will notify the Sponsor of any follow-up information in the eCRF pages within 24 hours of new information awareness (see [section 9.2.1](#)).

#### **9.4. Procedure for SAE communication**

If required by applicable local regulations, the Investigator will promptly notify the relevant IRB/IEC (in addition to the Sponsor) of any SAE (including post-study SAEs and follow-up information) that occurred at their site or was brought to their attention by the Sponsor. The Investigator will verify that the IRB/IEC acknowledges receipt of the notification.

In case of Suspected Unexpected Serious Adverse Reactions (SUSARs), unusual increase in the frequency or the severity of expected SAEs or new safety data which could have an impact on the overall expectedness of a SAR or change in the safety profile of the investigational product(s) that requires the informed consent to be updated, the Sponsor will prepare investigator safety reports according to regulatory requirements relating to safety reporting.

This report will be communicated by the Sponsor to all the investigators involved in clinical studies with Debio-1143 to ensure that any ongoing subjects can be promptly informed.

#### **9.5. Pregnancies**

Pregnancies should be avoided during the study. Any patient who nevertheless becomes pregnant must be followed-up until pregnancy outcome is known.

Pregnancies shall be reported from the Investigational site to the Sponsor using a Pregnancy Report Form. The same process and timelines as defined for SAE reporting apply ([section 9.2.1](#)). In case of serious outcomes experienced by the parent and/or the fetus/child (definition of ‘seriousness’ in [section 9.1.2](#)), the events should be reported as SAEs using the SAE report form. This procedure applies to pregnancies in female patients as well as to those in female partners of male patients.

### **10. MONITORING AND STUDY COMMITTEES**

#### **10.1. Monitoring**

The study Sponsor is Debiopharm International S.A (DPI), Lausanne, Switzerland.

A designated Contract Research Organization (CRO) will perform site monitoring.

At mutually convenient times during the study, the Investigator will let DPI or its representative review all eCRFs and related source documentation, i.e., patient office, hospital, clinic, and laboratory records.

At timely intervals, and at the closing of the study, all IMPs will be accounted for and dispensing records made available to DPI or its representative (see also [sections 7.3](#) and [7.6](#)).

In case eCRFs require support information, DPI may request copies of patient records or other source documents. All the necessary steps will then be taken to protect patient identity. Adherence to local and national laws governing protection of patient identity will be ensured.

#### **10.2. Study committees**

##### **10.2.1. Data Safety Monitoring Committee**

A Data Safety Monitoring Committee (DSMC) will overview study conduct during both parts A and B. It will be composed of at least all actively involved investigators (or their designee), the Sponsor Medical Director and the CRO medical monitor as voting members and will meet regularly to overview the clinical safety of the patients, laboratory data and the conduct of the study. Ad hoc members may be invited as needed.

During Part A, calls will be scheduled monthly or according to patient recruitment as necessary. A charter will be provided as a separate document.

During part B the DSMC will meet approximately every three months, but more frequently if needed due to rapid recruitment. A charter will be provided separately.

